### **Missing data analysis**

*Table 25 Missing data analysis*

MPOPostOp	off-pump CABG (N=181)	on-pump CABG (N=128)	pump-assisted CABG (N=27)
Present	153 (84.5)	102 (79.7)	14 (51.9)
Missing	28 (15.5)	26 (20.3)	13 (48.1)

CABG – coronary artery bypass grafting.

Reason of missingness: laboratory test shows exceeding upper scale limit. Results could be biased.

Hypothesis: postoperative MPO level too high to determine with current assay.

Hypothesis testing: new clinical trial with larger number of patients could this hypothesis tested.

### Secondary Endpoint Analysis

Hypothesis testing:

- Normality test (Kolmogorov-Smirnov test, Shapiro-Wilk test)

Group comparing:

Continuous variables

- Non-normal distribution: Kruskal-Wallis test with adjustment for multiple comparisons

*Table 29 Postoperative characteristics*

Variables	off-pump CABG (N=181)	on-pump CABG (N=128)	pump-assisted CABG (N=27)	P Value
ICU days				<.0001*
Mean±SD	2.5±2.2	3.1±3.1	3.3±1.9	
Min–Max	1.0–20.0	1.0–26.0	2.0–7.0	
Median (IQR)	2.0 (1.0–2.0)	2.0 (2.0–3.0)	2.0 (2.0–5.0)	
Days in hospital after CABG				0.0066*
Mean±SD	12.6±6.1	13.6±5.5	12.9±4.1	
Min–Max	0.0–50.0	0.0–33.0	3.0–25.0	
Median (IQR)	12.0 (10.0–13.0)	13.0 (11.0–15.0)	13.0 (10.0–15.0)	
Vasopressor and inotrope demand				0.0204*
Mean±SD	0.1±0.5	0.2±0.9	0.2±0.5	
Min–Max	0.0–4.2	0.0–8.4	0.0–2.1	
Median (IQR)	0.0 (0.0–0.1)	0.0 (0.0–0.1)	0.0 (0.0–0.1)	
Levosimendan demand				0.0220*
Mean±SD	0.0±0.1	0.2±1.8	0.7±3.8	
Min–Max	0.0–0.8	0.0–20.0	0.0–20.0	

Variables	off-pump CABG (N=181)	on-pump CABG (N=128)	pump-assisted CABG (N=27)	P Value
Median (IQR)	0.0 (0.0–0.0)	0.0 (0.0–0.0)	0.0 (0.0–0.0)	
Lenght of pulmonary ventilation				0.0181*
Mean±SD	1.2±1.2	1.5±1.6	1.4±0.7	
Min–Max	0.0–14.0	0.0–13.0	1.0–3.0	
Median (IQR)	1.0 (1.0–1.0)	1.0 (1.0–1.0)	1.0 (1.0–2.0)	
ESV after CABG				0.1283*
Nmiss (%)	22 (12.2)	22 (17.2)	3 (11.1)	
Mean±SD	42.7±23.5	45.2±21.0	50.9±32.2	
Min–Max	10.0–149.0	19.0–155.0	19.0–170.0	
Median (IQR)	37.0 (27.0–50.0)	40.5 (31.0–52.0)	40.5 (34.0–52.5)	
EDV after CABG				0.0508*
Nmiss (%)	22 (12.2)	22 (17.2)	3 (11.1)	
Mean±SD	103.7±37.7	107.2±32.6	122.3±40.4	
Min–Max	41.0–243.0	44.0–212.0	73.0–222.0	
Median (IQR)	97.0 (79.0–122.0)	106.0 (81.0–131.0)	109.5 (96.0–136.5)	
EF after CABG				0.9820*
Nmiss (%)	22 (12.2)	21 (16.4)	4 (14.8)	
Mean±SD	59.6±10.3	59.8±7.7	60.5±12.3	
Min–Max	29.0–86.0	28.0–73.0	23.0–88.0	
Median (IQR)	61.0 (54.0–66.0)	61.0 (58.0–65.0)	60.0 (55.0–67.0)	
End Systolic Volume				0.4178*
Nmiss (%)	5 (2.8)	5 (3.9)		
Mean±SD	48.0±28.0	46.8±23.0	50.5±20.7	
Min–Max	11.0–178.0	12.0–138.0	23.0–107.0	

Variables	off-pump CABG (N=181)	on-pump CABG (N=128)	pump-assisted CABG (N=27)	P Value
Median (IQR)	40.5 (31.0–55.0)	43.0 (32.0–54.0)	44.0 (38.0–55.0)	
Low Cardiac Output Syndrome				0.39 45*
No	166 (91.7)	113 (88.3)	26 (96.3)	
Yes	15 (8.3)	15 (11.7)	1 (3.7)	
Reoperation Cardio				0.83 61**
No	176 (97.2)	126 (98.4)	27 (100)	
Yes	5 (2.8)	2 (1.6)		
Reoperation non cardio				0.07 40**
No	177 (97.8)	119 (93.0)	27 (100)	
Yes	4 (2.2)	9 (7.0)		
Kidney Damage				<.00 01**
Cr< URL	130 (71.8)	52 (40.6)	17 (63.0)	
Cr> 25% URL	49 (27.1)	70 (54.7)	7 (25.9)	
Hemodialysis				
2 (1.1)	6 (4.7)	3 (11.1)		
Atrial fibrillation				0.07 84**
No	155 (85.6)	101 (78.9)	19 (70.4)	
Yes	26 (14.4)	27 (21.1)	8 (29.6)	
Multiorgan dysfunction after CABG				0.00 17**
No	179 (98.9)	116 (90.6)	25 (92.6)	
Yes	2 (1.1)	12 (9.4)	2 (7.4)	
Infection or leukocytosis or febril >7 days				0.86 34**
No	166 (91.7)	117 (91.4)	26 (96.3)	
Yes	15 (8.3)	11 (8.6)	1 (3.7)	
Bleeding after CABG				0.00 14**
No	178 (98.3)	114 (89.1)	26 (96.3)	
Yes	3 (1.7)	14 (10.9)	1 (3.7)	
Graft thrombosis within 30d after CABG				0.82 95**
No	175 (96.7)	122 (95.3)	26 (96.3)	

Variables	off-pump CABG (N=181)	on-pump CABG (N=128)	pump-assisted CABG (N=27)	P Value
Yes	6 (3.3)	6 (4.7)	1 (3.7)	
Pulmonary dysfunction after CABG				0.04 92**
No	171 (94.5)	117 (91.4)	21 (80.8)	
Yes	10 (5.5)	11 (8.6)	5 (19.2)	
Neurological complications within 30d after CABG				0.03 22**
No	175 (96.7)	124 (96.9)	23 (85.2)	
Yes	6 (3.3)	3 (2.3)	3 (11.1)	
Death within 30d after CABG				0.25 45**
No	177 (97.8)	121 (94.5)	27 (100)	
Yes	4 (2.2)	7 (5.5)		
Intestinal complications within 30d after CABG				0.27 73**
No	180 (99.4)	127 (99.2)	26 (96.3)	
Yes	1 (0.6)	1 (0.8)	1 (3.7)	

\* Kruskal-Wallis test, \*\* exact Fisher's test. Nmiss – number of missing values, SD – standard deviation, IQR – interquartile range, CABG – coronary artery bypass grafting

Table 30 Troponin I level after CABG

Variables	off-pump CABG (N=181)	on-pump CABG (N=128)	pump-assisted CABG (N=27)	P Value
TnI before CABG				0.0938
Nmiss (%)	145 (80.1)	99 (77.3)	19 (70.4)	
Mean±SD	0.0±0.1	0.0±0.1	0.0±0.0	
Min–Max	0.0–0.5	0.0–0.2	0.0–0.1	
Median (IQR)	0.0 (0.0–0.0)	0.0 (0.0–0.0)	0.0 (0.0–0.1)	
TnI 1st day				<.0001
Nmiss (%)	17 (9.4)	10 (7.8)	1 (3.7)	
Mean±SD	2.5±8.9	6.0±10.3	4.7±7.3	
Min–Max	0.0–98.0	0.0–93.0	0.3–31.1	
Median (IQR)	0.4 (0.2–1.0)	3.1 (1.8–6.3)	1.4 (0.7–6.8)	
TnI 2st day				<.0001
Nmiss (%)	104 (57.5)	39 (30.5)	9 (33.3)	
Mean±SD	3.5±8.2	3.9±7.9	4.5±5.9	

Date of the document 06 December 2016

Variables	off-pump CABG (N=181)	on-pump CABG (N=128)	pump-assisted CABG (N=27)	P Value
Min–Max	0.0–50.0	0.0–50.0	0.2–18.8	
Median (IQR)	0.4 (0.2–2.1)	1.5 (0.7–3.4)	0.9 (0.4–6.1)	
TnI 3st day				0.1936
Nmiss (%)	149 (82.3)	90 (70.3)	21 (77.8)	
Mean±SD	3.4±7.4	2.5±2.8	4.8±4.5	
Min–Max	0.1–40.7	0.1–14.6	0.5–10.9	
Median (IQR)	1.1 (0.2–3.5)	1.4 (0.6–3.5)	2.6 (1.9–10.0)	
TnI 4st day				0.3843
Nmiss (%)	168 (92.8)	108 (84.4)	22 (81.5)	
Mean±SD	5.4±7.5	2.3±3.0	2.7±3.2	
Min–Max	0.0–27.9	0.1–10.7	0.2–8.3	
Median (IQR)	3.2 (1.3–7.5)	0.9 (0.4–2.6)	1.5 (1.4–2.0)	
TnI 5st day				0.2222
Nmiss (%)	158 (87.3)	106 (82.8)	23 (85.2)	
Mean±SD	1.5±2.1	0.9±1.4	2.4±1.9	
Min–Max	0.0–6.6	0.0–5.9	0.5–4.9	
Median (IQR)	0.3 (0.0–2.5)	0.4 (0.1–0.8)	2.2 (1.2–3.7)	

Table 30 Troponin I level after CABG in patients without low cardiac output syndrome after CABG

Variables	off-pump CABG (N=166)	on-pump CABG (N=113)	pump-assisted CABG (N=26)	P Value
MPO before operation				0.3871
Nmiss (%)	27 (16.3)	18 (15.9)	9 (34.6)	
Mean±SD	36.0±32.6	38.8±29.5	29.0±15.3	
Min–Max	2.8–237.8	4.1–168.9	5.6–65.4	
Median (IQR)	28.1 (16.4–40.6)	30.8 (19.3–47.7)	28.7 (18.7–34.0)	
MPO after operation				0.3871
Nmiss (%)	27 (16.3)	18 (15.9)	9 (34.6)	
Mean±SD	36.0±32.6	38.8±29.5	29.0±15.3	
Min–Max	2.8–237.8	4.1–168.9	5.6–65.4	
Median (IQR)	28.1 (16.4–40.6)	30.8 (19.3–47.7)	28.7 (18.7–34.0)	
TnI before CABG				0.0403

Date of the document 06 December 2016

Variables	off-pump CABG (N=181)	on-pump CABG (N=128)	pump-assisted CABG (N=27)	P Value
Nmiss (%)	134 (80.7)	89 (78.8)	18 (69.2)	
Mean±SD	0.0±0.1	0.0±0.1	0.0±0.0	
Min–Max	0.0–0.5	0.0–0.2	0.0–0.1	
Median (IQR)	0.0 (0.0–0.0)	0.0 (0.0–0.0)	0.0 (0.0–0.1)	
TnI 1st day				<.0001
Nmiss (%)	14 (8.4)	8 (7.1)	1 (3.8)	
Mean±SD	1.1±2.6	4.1±4.0	4.1±7.0	
Min–Max	0.0–18.5	0.0–18.7	0.3–31.1	
Median (IQR)	0.4 (0.2–0.7)	2.5 (1.7–5.0)	1.4 (0.7–2.7)	
TnI 2st day				<.0001
Nmiss (%)	100 (60.2)	37 (32.7)	9 (34.6)	
Mean±SD	1.9±4.7	2.3±3.0	3.9±5.5	
Min–Max	0.0–29.8	0.0–15.0	0.2–18.8	
Median (IQR)	0.3 (0.1–1.0)	1.2 (0.6–2.5)	0.9 (0.4–5.9)	
TnI 3st day				0.0828
Nmiss (%)	140 (84.3)	84 (74.3)	21 (80.8)	
Mean±SD	1.4±2.0	1.8±1.8	3.5±3.7	
Min–Max	0.1–9.2	0.1–6.5	0.5–10.0	
Median (IQR)	0.6 (0.2–2.1)	1.1 (0.5–2.9)	2.3 (1.9–3.0)	
TnI 4st day				0.6389
Nmiss (%)	158 (95.2)	99 (87.6)	21 (80.8)	
Mean±SD	2.6±3.1	2.0±2.7	2.7±3.2	
Min–Max	0.0–9.1	0.1–8.3	0.2–8.3	
Median (IQR)	1.6 (0.3–4.1)	0.8 (0.4–2.6)	1.5 (1.4–2.0)	
TnI 5st day				0.0541
Nmiss (%)	149 (89.8)	96 (85.0)	22 (84.6)	
Mean±SD	0.8±1.6	0.7±1.0	2.4±1.9	
Min–Max	0.0–5.8	0.0–3.8	0.5–4.9	
Median (IQR)	0.1 (0.0–0.9)	0.3 (0.1–0.8)	2.2 (1.2–3.7)	

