[[contact]](mailto:[contact]) [contact]

Date of the document 06 December 2016

Type of trial	Prospective non-randomised single-centre
Type of research	Exploratory
Timeline	2015-2019
Groups	Off-pump  On – pump  Pump-assisted (on-pump without aortic cross-clamping)
Sample size estimation	> 300 patients
Planned sample size	Average: 300  Off-pump: 100  On-pump: 100  Pump-assisted: 100
Actual sample size	Average: 336  Off-pump: 181 (conversion 6)  On-pump: 128  Pump-assisted: 27
Baseline characteristics comparing	Testing for type of distribution of baseline characteristics:  ANOVA for normal distribution  Kruskal-Wallis test with multiple groups comparison adjustment for non-normal distribution  Chi-squared test or exact Fisher's test for nominal data
Statistics hypothesis testing	ANOVA/ANCOVA for MPO level, troponin I level
Missing Data Handling	Drop observations with missing data
Evaluating of reason of missingness	Hypothesis: Missing data depend on severity of complications  Hypothesis testing with logistic regression model: Missingness = complications

Assessment of Myocardial Ischemic-Reperfusion Injury During Off- and On- Pump CABG  
(ClinicalTrials.gov Identifier: NCT03050489). Corresponding author: [name]  
[[contact]](mailto:[contact]) [contact]

Date of the document 06 December 2016

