### **Patients allocation**

Patients were allocated into one of three groups of treatment by Heart Team. Patients consecutively admitted in the Department of Cardiac Surgery #1 and #2. All patients who admitted in the Department of Cardiac Surgery #1 allocated into off-pump CABG group. Patients who admitted in the Department of Cardiac Surgery #2 allocated into off-pump CABG group, on-pump CABG group (when have proximal lesions of RCA or LCx), off-pump CABG group (when have more distal lesion of coronary arteries) or pump-assisted CABG group (when have difusse coronary artery lesions). Heart Team includes three or more cardiac surgeons who performs off-pump, on-pump or pump-assisted CABG more than 10 years, two or more interventional cardiologists, one neurologist, two or more anesthesiologist, two or more reanimatologist, one perfusologist and two cardiologist. After debating patients were alocated into one of threy groups for elective CABG.

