# Assessment of Myocardial Ischemic-Reperfusion Injury During Off- and On- Pump CABG

(ClinicalTrials.gov Identifier: NCT03050489). Corresponding author: [name]

[[contact]](mailto:[contact]) [contact]

Date of the document 06 December 2016

- To compare inotrope and vasopressor agents demand after off-pump CABG, on-pump CABG and pump-assisted CABG (with cardiopulmonary bypass without aortic cross-clamping)
- To compare duration of pulmonary ventilation after off-pump CABG, on-pump CABG and pump-assisted CABG (with cardiopulmonary bypass without aortic cross-clamping)
- To compare end systolic volume, end diastolic volume, ejection fraction after off-pump CABG, on-pump CABG and pump-assisted CABG (with cardiopulmonary bypass without aortic cross-clamping)
- To investigate whether MPO level could predict outcomes after CABG
- To compare incidence of reoperation after off-pump CABG, on-pump CABG and pump-assisted CABG (with cardiopulmonary bypass without aortic cross-clamping)
- To compare incidence of renal dysfunction after off-pump CABG, on-pump CABG and pump-assisted CABG (with cardiopulmonary bypass without aortic cross-clamping)
- To compare incidence of atrial fibrillation after off-pump CABG, on-pump CABG and pump-assisted CABG (with cardiopulmonary bypass without aortic cross-clamping)
- To compare incidence of death during 30 days after off-pump CABG, on-pump CABG and pump-assisted CABG (with cardiopulmonary bypass without aortic cross-clamping)
- To compare incidence of stroke during 30-days after off-pump CABG, on-pump CABG and pump-assisted CABG (with cardiopulmonary bypass without aortic cross-clamping)

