Median (IQR)	62.0 (55.0–67.0)	62.0 (59.0–66.0)	63.0 (55.0–65.0)	
End diastolic volume				0.2187
Nmiss (%)	5 (2.8)	5 (3.9)		
Mean±SD	115.7±41.5	115.7±34.8	131.1±53.6	
Min–Max	11.0–270.0	44.0–224.0	81.0–367.0	
Median (IQR)	109.0 (91.0–131.5)	114.0 (90.0–139.0)	121.0 (101.0–141.0)	
End Systolic Volume				0.4178
Nmiss (%)	5 (2.8)	5 (3.9)		
Mean±SD	48.0±28.0	46.8±23.0	50.5±20.7	
Min–Max	11.0–178.0	12.0–138.0	23.0–107.0	

Assessment of Myocardial Ischemic-Reperfusion Injury During Off- and On- Pump CABG

(ClinicalTrials.gov Identifier: NCT03050489). Corresponding author: [name]

[[contact]](mailto:[contact]) [contact]

Date of the document 06 December 2016

Variables	off-pump CABG (N=181)	on-pump CABG (N=128)	pump-assisted CABG (N=27)	P Value
Median (IQR)	40.5 (31.0–55.0)	43.0 (32.0–54.0)	44.0 (38.0–55.0)	
Gender				0.6268***
Male	142 (78.5)	95 (74.2)	20 (74.1)	
Female	39 (21.5)	33 (25.8)	7 (25.9)	

\* ANOVA, \*\* Kruskal-Wallis test, Nmiss – number of missing values, SD – standard deviation, IQR – interquartile range, \*\*\* - Chi-squared test, CABG – coronary artery bypass grafting

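### Post-operative EDV, ESV and EF are compared between non-randomised groups without the pre-operative values that were collected; for EDV, pump-assisted versus off-pump, much of the gap may pre-date surgery

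*Combined protocol and SAP*

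**What the plan says.** One of the Secondary objectives is "To compare end systolic volume, end diastolic volume, ejection fraction after off-pump CABG, on-pump CABG and pump-assisted CABG". Under Secondary Endpoint Analysis the only between-group method for continuous variables is "Non-normal distribution: Kruskal-Wallis test with adjustment for multiple comparisons". Table 29 then prints p=0.0508 for EDV, p=0.1283 for ESV and p=0.9820 for EF, each on the post-operative value with no covariate, change score or stratification.

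The synopsis (Table 2) confines model-based analysis to "ANOVA/ANCOVA for MPO level, troponin I level". Table 4 lists pre-operative EDV, ESV and EF as database variables, but they are used only for the baseline comparison in Table 5.

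Under Patients allocation, the Heart Team chooses the technique partly on coronary anatomy, for example "pump-assisted CABG group (when have difusse coronary artery lesions".

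Table 29, whose title announces postoperative characteristics, also holds a second ESV row. Every figure in it, including p=0.4178, is that of the pre-operative ESV row in Table 5.

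**The concern.** Without randomisation, nothing in the design makes the groups alike in ventricular size or function before surgery. A test on the post-operative value alone cannot separate a difference the patients brought with them from one that followed the operation. The patient's own pre-operative measurement is the most direct covariate for this and is already in the database. The SAP uses this approach elsewhere: its model for post-operative MPO includes pre-operative MPO.

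Two things are at stake. One is bias, if the groups differed beforehand. The other is precision: if the pre-post correlation is r, adjustment multiplies the standard error by about √(1 - r²). The repeated ESV row is a separate reporting fault. It leaves Table 29 with two ESV results, one of which is not post-operative.

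**Working it through.** **Inputs (Tables 5 and 29; n = group size minus missing).**

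| EDV | Off-pump | On-pump | Pump-assisted | Printed p |
|---|---|---|---|---|
| Before, mean±SD (n) | 115.7±41.5 (176) | 115.7±34.8 (123) | 131.1±53.6 (27) | 0.2187 |
| After, mean±SD (n) | 103.7±37.7 (159) | 107.2±32.6 (106) | 122.3±40.4 (24) | 0.0508 |
| Before, median | 109.0 | 114.0 | 121.0 | |
| After, median | 97.0 | 106.0 | 109.5 | |

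**The plan's own figure.** The Kruskal-Wallis p of 0.0508 needs patient-level ranks and cannot be reproduced from summaries. As a plausibility check only, one-way ANOVA from the means, SDs and n gives p=0.063 after surgery and p=0.165 before.

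**Availability of baseline.** EDV and ESV: (336 - 10)/336 = 97.0% overall, and 123/128 = 96.1% on-pump. EF: (336 - 3)/336 = 99.1%.

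**Gap before and after, EDV, pump-assisted minus off-pump.**
- Means: 131.1 - 115.7 = 15.4 before; 122.3 - 103.7 = 18.6 after; 15.4/18.6 = 0.83.
- Medians: 121.0 - 109.0 = 12.0 before; 109.5 - 97.0 = 12.5 after.
- Approximate 95% CI for the pre-operative mean gap: -5.7 to 36.5.

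**How far one value matters.** The pump-assisted pre-operative maximum is 367.0. Without it the mean is (27 × 131.1 - 367)/26 = 122.0, the gap is 122.0 - 115.7 = 6.3, and 6.3/18.6 = 34%.

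**Other contrasts, means.**
- ESV, pump-assisted minus off-pump: 50.5 - 48.0 = 2.5 before; 50.9 - 42.7 = 8.2 after; ratio 30%.
- EF, same contrast: 58.4 - 60.2 = -1.8 before; 60.5 - 59.6 = +0.9 after; the sign reverses.
- EDV, on-pump minus off-pump: 0.0 before; 107.2 - 103.7 = 3.5 after.
- EDV, pump-assisted minus on-pump: 15.4 before; 122.3 - 107.2 = 15.1 after.

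**Approximate adjusted EDV difference, pump-assisted minus off-pump.** Pooled SDs over the three groups are 40.3 before and 36.1 after. The correlation r is not in the documents; 0.5 to 0.8 is an assumption.
- Slope b = r × 36.1/40.3; adjusted difference = 18.6 - b × 15.4.
- Unadjusted SE = 36.1 × √(1/24 + 1/159) = 7.9; adjusted SE = 7.9 × √(1 - r²).

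| r | b | Difference | SE | 95% CI |
|---|---|---|---|---|
| none (unadjusted) | – | 18.6 | 7.9 | 3 to 34 |
| 0.5 | 0.45 | 11.7 | 6.9 | -2 to 25 |
| 0.8 | 0.72 | 7.5 | 4.7 | -2 to 17 |

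**Same calculation without the 367.0.** Removing it takes the pump-assisted pre-operative SD to √[(26 × 53.6² - (27/26) × 235.9²)/25] = 26.0 and the pooled SD to 38.0. The adjusted difference is then 18.6 - 0.475 × 6.3 = 15.6 (2 to 29) at r=0.5, and 18.6 - 0.76 × 6.3 = 13.8 (4 to 23) at r=0.8.

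**The case against.** The strongest reply is that the striking figure comes from one contrast of one endpoint. It does not extend to mean ESV or mean EF, and the two large groups (off-pump and on-pump) have the same pre-operative mean EDV. That is correct, and 83% should not be read as a general result.

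The figure is also fragile. The pre- and post-operative means come from different patient sets. The largest post-operative pump-assisted EDV is 222.0, with three values missing, so the patient with 367.0 either fell by at least 145 or has no post-operative echo. In the second case that value would not enter a paired analysis at all. This stands against the size, but not against the direction: the medians, which one extreme value hardly moves, show nearly the same gap before and after.

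A reader might infer that pump-assisted patients are shown to have larger ventricles at entry. The documents do not establish this: the overall pre-operative p is 0.2187, the interval for the gap includes zero, and nothing links diffuse coronary lesions to dilatation. Equally, a non-significant baseline test with 27 patients in one group does not show balance or remove the reason to adjust.

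A reader might also infer that the plan credits the operation with pre-existing dilatation. No summary in the document attributes EDV, ESV or EF differences to technique. The risk lies in how the printed p values will be read.

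**Conclusion.** The concern holds in a limited form. The comparison of post-operative EDV, ESV and EF ignores measured pre-operative values in groups formed by clinical choice, and this should be corrected.

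For EDV, pump-assisted versus off-pump, much of the post-operative gap appears to have been present before surgery. The medians support that direction; the 83% on means is descriptive. For mean ESV and EF, and for off-pump versus on-pump EDV, the argument is the non-random design and a standard error about 13% (r=0.5) to 40% (r=0.8) smaller.

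It is tempting to conclude that adjustment would remove the EDV signal. The summaries do not settle that. With all values, the approximate adjusted intervals include zero; without the single 367.0 they do not. Both rest on an assumed correlation and on unpaired means, so only the patient-level analysis can give the adjusted difference.

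The study is labelled exploratory and these are secondary endpoints. The primary MPO result is not affected.

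**What to change.** For each of EDV, ESV and EF, fit an ANCOVA of the post-operative value on technique plus the pre-operative value of the same variable, in patients with both measurements. Report an adjusted estimate with a 95% CI for each pair of techniques, as a difference on the raw scale or a ratio on the log scale if the data are skewed. Use rank ANCOVA only as a sensitivity test, since it gives no difference in volume units. State whether the patient with the pre-operative EDV of 367.0 is in the paired set.

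Remove from Table 29 the ESV row with p=0.4178, which belongs to Table 5.

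The cost is three models on existing variables. Beyond those already without a post-operative echo, at most 10 patients are lost for EDV and ESV and 3 for EF. Adjusting for one baseline variable will not remove all confounding by the choice of technique, and the text should say so.

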#### Abbreviations

AEs – Adverse events

CABG – coronary artery bypass grafting

CPB – cardiopulmonary bypass grafting

ECG – elecrocardiogram

IL-8 - interleukin 8

IQR – interquartile range

LCx – left circumflex artery

LDL - low-density lipoprotein

MPO – myeloperoxidase

Nmiss – number of missing values

RCA – right coronary artery

Rpm – rate per minute

SAE - Serious Adverse Event

URL – upper reference limit

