## Study Design

Prospective single center non-randomized clinical trial.

**Study Centers:** First Saint Petersburg State Medical University.

**Number of groups:** 3

Intervention:

Group 1: off-pump CABG

Group 2: on-pump CABG

Group 3: pump-assisted CABG (on-pump CABG without aortic cross-clamping)

**Sample size:** >300.

*Table 3 Number of patients*

Intervention	Number of patients	
	Planned	Actual
off-pump CABG	100	181 (175)
on-pump CABG	100	128 (127)
pump-assisted CABG	100	27 (33)
Total	300	336
Conversion	N/A	6

181 patient planned for elective CABG. There were 6 conversions to pump – assisted CABG (on-pump CABG without aortic cross-clamping). 175 received off-pump-CABG. 27 patient planned for elective pump – assisted CABG (on-pump CABG without aortic cross-clamping). 33 pump – assisted CABG were performed.

**Primary Endpoint:** MPO level after operation.

**Secondary Endpoints:** low output syndrome, length of stay in intensive care unit, length of stay in hospital, inotrope and vasopressor agents demand, duration of pulmonary ventilation, end systolic volume, end diastolic volume, ejection fraction, reoperation, renal dysfunction, atrial fibrillation, death during 30 days after CABG, stroke during 30-days after CABG.

Assessment of Myocardial Ischemic-Reperfusion Injury During Off- and On- Pump CABG (ClinicalTrials.gov Identifier: NCT03050489). Corresponding author: [name] [[contact]](mailto:[contact]) [contact]

Date of the document 06 December 2016

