#### **Baseline Characteristics**

**Hypothesis: baseline characteristics are comparable between groups.**

Hypothesis testing:

- Normality test (Kolmogorov-Smirnov test, Shapiro-Wilk test)

Assessment of Myocardial Ischemic-Reperfusion Injury During Off- and On- Pump CABG (ClinicalTrials.gov Identifier: NCT03050489). Corresponding author: [name] [[contact]](mailto:[contact]) [contact]

Date of the document 06 December 2016

Group comparing:

Continuous variables

- Non-normal distribution: Kruskal-Wallis test with adjustment for multiple comparisons
- Normal distribution: t-test with multiple comparison adjustment

Nominal variables

- Chi-squared test/ Fisher's exact test

Baseline characteristics:

*Table 4 Baseline characteristics specification*

Characteristic	Variable name in database	Test
Age	Age	t-test
Gender	Sex	Chi-squared test/ exact Fisher's test
Syntax Score I	SS1	Kruskal-Wallis test
Syntax Score II	SS2	Kruskal-Wallis test
Euroscore II	EII	Kruskal-Wallis test
Charlson/ Deyo Index	ICD	Kruskal-Wallis test
Ejection Fraction	EFPreOp	Kruskal-Wallis test
End diastolic volume	EDVPreOp	Kruskal-Wallis test
End systolic volume	ESVPreOp	Kruskal-Wallis test

*Table 5 Baseline characteristics*

Variables	off-pump CABG (N=181)	on-pump CABG (N=128)	pump-assisted CABG (N=27)	P Value
Age in years				0.7836*
Mean±SD	63.5±7.3	63.6±7.1	64.3±8.9	
Min–Max	43.0–79.0	33.0–80.0	46.0–80.0	
Median (IQR)	63.0 (59.0–68.0)	64.0 (59.0–68.0)	66.0 (58.0–69.0)	
Syntax Score I				0.3667**
Nmiss (%)	1 (0.6)	2 (1.6)	1 (3.7)	

Variables	off-pump CABG (N=181)	on-pump CABG (N=128)	pump-assisted CABG (N=27)	P Value
Mean±SD	26.2±9.4	27.4±7.7	27.8±6.7	
Min–Max	2.0–61.0	10.0–52.5	14.0–43.5	
Median (IQR)	24.4 (22.0–31.8)	25.8 (22.0–31.5)	27.0 (22.0–33.0)	
Syntax Score II				0.6002
Nmiss (%)	1 (0.6)	2 (1.6)	1 (3.7)	
Mean±SD	41.7±11.6	40.9±12.5	43.5±11.6	
Min–Max	8.1–68.0	3.7–68.3	24.6–67.6	
Median (IQR)	41.4 (32.7–50.8)	42.3 (31.1–49.9)	43.5 (34.5–53.6)	
EuroScore I				0.3137
Mean±SD	1.4±1.3	1.3±1.0	1.4±1.4	
Min–Max	0.5–10.8	0.5–5.5	0.5–6.7	
Median (IQR)	1.0 (0.7–1.5)	1.0 (0.6–1.5)	0.8 (0.6–1.4)	
Index Charlson/Deyo				0.1141
Nmiss (%)	1 (0.6)			
Mean±SD	5.4±2.0	5.0±1.8	4.9±2.0	
Min–Max	1.0–11.0	0.0–10.0	2.0–10.0	
Median (IQR)	5.0 (4.0–7.0)	5.0 (4.0–6.0)	5.0 (4.0–6.0)	
Ejection Fraction before operation				0.9090
Nmiss (%)	1 (0.6)	2 (1.6)		
Mean±SD	60.2±10.4	60.9±8.5	58.4±11.7	
Min–Max	30.0–85.0	28.0–85.0	30.0–72.0	

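### Table 29 grades renal dysfunction on post-operative creatinine against a laboratory limit with no pre-operative value, so as printed it is a prevalence and not the planned incidence, and its grades are not contiguous

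*Combined protocol and SAP*

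**What the plan says.** Study Design lists the endpoint by name only, among "reoperation, renal dysfunction, atrial fibrillation, death during 30 days after CABG". Secondary objectives makes it an incidence: "To compare incidence of renal dysfunction after off-pump CABG, on-pump CABG and pump-assisted CABG". The Definitions section gives no criterion, threshold, reference value or sampling day for it.

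The only operational form is the Kidney Damage row in Secondary Endpoint Analysis, under "Table 29 Postoperative characteristics". It has three grades, with counts in the order off-pump, on-pump, pump-assisted:

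- "Cr< URL 130 (71.8) 52 (40.6) 17 (63.0"
- "Cr> 25% URL 49 (27.1) 70 (54.7) 7 (25.9"
- hemodialysis, "2 (1.1) 6 (4.7) 3 (11.1"

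The Abbreviations list gives "URL – upper reference limit". The row is tested by Fisher's exact test, with p below 0.0001.

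The list headed "Table 4 Baseline characteristics specification" covers age, sex, the Syntax, Euroscore and Charlson/Deyo scores, ejection fraction and ventricular volumes. Neither it nor Table 5 has creatinine, filtration rate or kidney disease as a variable. Exclusion criteria names valve disease and acute or urgent cases, not renal disease. Patients allocation describes assignment by department and coronary anatomy, without randomisation.

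**The concern.** An incidence counts new events. A post-operative value set against a fixed laboratory limit counts everyone above the limit, whether or not surgery put them there. Ejection fraction, ventricular volumes, MPO and troponin each have a pre-operative figure in the document; renal function has none, so the reader cannot separate new injury from prior disease.

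The labels raise a second problem. One grade stops at the URL and the next starts 25% above it. A patient between the two has no grade, yet no patient is left ungraded.

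This row matters because it shows the largest group difference of any complication in Table 29, and the smallest p-value among them. If the rates are quoted as incidence, they claim more than the printed rule can support.

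**Working it through.** **Inputs.** Table 29 counts (below URL / above 25% / dialysis): off-pump 130 / 49 / 2, on-pump 52 / 70 / 6, pump-assisted 17 / 7 / 3.

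**Step 1: reproduce the table.** Totals are 130 + 49 + 2 = 181, 52 + 70 + 6 = 128 and 17 + 7 + 3 = 27, the full group sizes. All nine percentages reproduce. The exact test on the 3×3 table gives p = 8.8 × 10⁻⁸ (chi-squared 37.1 on 4 df, p = 1.7 × 10⁻⁷), in agreement with the printed value.

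**Step 2: any kidney damage (upper two grades).**

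- Off-pump: 51/181 = 28.2%
- On-pump: 76/128 = 59.4%
- Pump-assisted: 10/27 = 37.0%

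On-pump minus off-pump = 0.594 − 0.282 = 0.312. SE = √(0.282 × 0.718/181 + 0.594 × 0.406/128) = 0.0548. The 95% CI is 0.312 ± 1.96 × 0.0548, or 20 to 42 points. The next largest spread between any two groups is 15.3 points, for atrial fibrillation (14.4% to 29.6%).

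**Step 3: what prior elevation would do.** The documents give no pre-operative prevalence, so what follows is algebra on an assumption and not an estimate. Let q be the share of a group already above the limit before surgery, and assume that these patients stay above it. Keep every patient in the denominator and remove them from the events:

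adjusted difference = 31.2 − (q on-pump − q off-pump), in points.

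- *Equal q, 0 to 25%.* The difference stays about 31 points (30.8 to 31.5 after rounding to whole patients). The rates do not: at q = 25%, off-pump falls from 28.2% to 6/181 = 3.3% and on-pump from 59.4% to 44/128 = 34.4%.
- *Equal q, also removed from the denominators.* The difference widens: 42/172 = 24.4% against 70/122 = 57.4% at q = 5%, which is 33.0 points.
- *Unequal q.* Each extra point of prior prevalence on-pump takes one point off the difference, and each extra point off-pump adds one. It takes 27 more prior cases on-pump (27/128 = 21 points), leaving 49/128 = 38.3% against 28.2%, before the two-group Fisher p exceeds 0.05 (p = 0.065).

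**Step 4: the labels.** The printed grades cover creatinine below the URL, more than 25% above it, and dialysis. The band from the URL to 25% above it is uncovered. Because the rows sum to every patient and no missing count is given, any patient in that band sits in a grade whose label does not describe them, or the labels do not state the rule used.

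**The case against.** The strongest reply is that the point rests on one abbreviated row label. The middle label could be shorthand for something else, such as a 25% rise from the patient's own value. In that case prior disease would not be counted, and the apparent gap would be loose labelling. The layout here is also disturbed (the hemodialysis label is separated from its counts), so a lost symbol cannot be ruled out. This stands as a limit on what can be asserted. It does not remove the defect: on that reading the grades mix two reference points, and the baseline values they need were used but not reported. Either way the rule must be stated.

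A reader might infer that the on-pump excess is produced by prior kidney disease, or that its size is uncertain about two-fold. The documents support neither. Assumed prevalences of 5% off-pump and 25% on-pump, with prior cases also removed from the denominators, give 21 points; 15% and 5% give 42. No source in the documents backs either pair, and both results lie within the sampling interval already shown. Allocation followed department and anatomy, not renal function. Charlson/Deyo (means 5.4, 5.0 and 4.9; p = 0.1141), EuroScore (p = 0.3137) and age (p = 0.7836) show no marked imbalance. That evidence does not establish renal balance, since composite scores cannot do so, but it gives no ground for assuming a large imbalance.

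It is also fair that the study is exploratory, that its stated conclusions make no renal claim, and that the row itself is headed Kidney Damage. The word incidence comes from the objective that the row is there to answer. Finally, Laboratory Test Abnormalities has captured results recorded under institutional procedures, so absence from Tables 4 and 5 does not show that pre-operative creatinine was never measured.

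**Conclusion.** The concern holds in a limited form. The endpoint is planned as an incidence, is undefined, and is reported by a rule that, read as printed, yields a post-operative prevalence. The 28.2%, 59.4% and 37.0% should not be called incidence. The number of patients with prior elevation is unknown, and the documents do not show that any such patient was counted.

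The 31-point difference (95% CI 20 to 42) is not shown to be wrong. With all patients kept in the denominator, equal prior prevalence leaves it about unchanged. Unequal prevalence would shift it point for point, in a direction that cannot be determined without baseline data.

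The gap from the URL to 25% above it is a defect of the labels or of the assignment rule. A reader might infer that patients were dropped, but the totals of 181, 128 and 27 rule that out. Nor do the documents say whether this row feeds the cumulative complication variable in the MPO and missingness models, so no effect there is claimed.

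**What to change.** 1. State the rule actually used to grade patients, with its reference value and sampling day. Make the labels contiguous, and correct any assignment that does not match the stated rule. Reassignment should wait until that rule is known.
2. Retrieve pre-operative creatinine for each patient and add it to Tables 4 and 5.
3. Re-run the row as new renal dysfunction: worsening from the patient's own pre-operative value by a threshold that the sponsor states, or new dialysis. Mark it post hoc and show it beside the row as now printed.
4. List patients with prior elevation separately, but do not exclude them. Under a change-from-baseline definition exclusion is unnecessary, and it would discard new injury in those patients.
5. If baseline values cannot be retrieved, label the row as post-operative creatinine above limit and do not report it as incidence.

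The cost is one routine laboratory value per patient, assumed to be in hospital records for elective surgery, and one repeated analysis. The reported rates, and possibly the group difference, may become smaller.
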